CI	Confidence Interval
CL	Total clearance
C _{max}	Maximum observed serum concentration
CV	Coefficient of Variance
DSMB	Data Safety Monitoring Board
eCRF	electronic Case Report Form
FDA	Food and Drug Administration
FluPRO	Influenza Patient Reported Outcomes
HAI	Hemagglutinin inhibition assay
ICH	International Conference on Harmonization
LOCF	Last Observable Measurement Carried Forward
ITT	Intent-to-Treat

MedDRA	Medical Dictionary for Regulatory Activities
mITT	Modified Intent-to-Treat
PCS	Potentially Clinically Significant
PK	Pharmacokinetics
PT	Preferred Term
QTcF	QT interval, using Fridericia's correction
SAE	Serious Adverse Event
SAP	Statistical Analysis Plan
SD	Standard Deviation
SE	Standard Error
SOC	System Organ Class
$T_{1/2}$	Terminal elimination half-life
TEAE	Treatment Emergent AE
T_{max}	Time of C_{max}
V_d	Volume distribution
WHODrug	World Health Organization Drug Dictionary

1 INTRODUCTION

This Statistical Analysis Plan (SAP) describes the planned analysis and reporting for Visterra Inc. protocol VIS410-202, a Phase 2a Double-blind, Placebo-controlled Study to Assess the Safety and Tolerability of a Single Intravenous Dose of VIS410 in Subjects with Uncomplicated Influenza A Infection.

The structure and content of this SAP provides sufficient detail to meet the requirements identified by the Food and Drug Administration (FDA) and International Conference on Harmonization (ICH) of Technical Requirements for Registration of Pharmaceuticals for Human Use: E9 Guidance on Statistical Principles in Clinical Trials.

A kineticist will derive standard non-compartmental pharmacokinetics (PK) parameters. Their analysis will be described within this SAP, see Sec. 11. Any other PK/PD analyses, including population PK modeling, are beyond the scope of this document.

This SAP is based on the protocol Version 1.1 dated 14 September, 2016 and electronic Case Report Form (eCRF) version 2.0 dated 01 December 2016. In the event of future amendments to the protocol, or changes in the eCRFs, this SAP will be modified as necessary to account for changes relevant to the statistical analysis.

2 STUDY OBJECTIVES AND DESIGN

2.1 Study Objectives

2.1.1 Primary Objectives

Assess the safety and tolerability of a single intravenous (IV) dose of VIS410 in subjects with uncomplicated influenza infection

2.1.2 Secondary Objectives

- Evaluate the efficacy of 2 dose levels of VIS410 compared with placebo on the time to alleviation of clinical symptoms of acute uncomplicated influenza
- Evaluate the effect of 2 dose levels of VIS410 on severity of influenza infection
- Assess the pharmacokinetics of 2 dose levels of VIS410 in serum
- Assess the effects of 2 dose levels of VIS410 on viral shedding
- Assess the immunogenicity of 2 dose levels of VIS410

2.1.3 Exploratory Objectives

- Assess the pharmacokinetics of VIS410 from nasopharyngeal secretions
- Assess viral isolates to determine the emergence of VIS410-resistant viruses
- Assess correlations between virology, safety, pharmacokinetics, viral shedding, clinical symptoms, and other endpoints
- Assess the anti-influenza immune response

2.2 Trial Design

This is a Phase 2a randomized, double-blind, placebo-controlled study to be conducted in approximately 150 subjects with uncomplicated influenza. The study is designed to compare an

infusion of a single high (4000 mg) or low (2000 mg) IV dose of VIS410 against placebo (0.9% sodium chloride). Subjects will be assigned randomly in a ratio of 1:1:1. Eligible subjects will receive VIS410 2000 mg, VIS410 4000 mg, or placebo administered as a single IV infusion over 2 hours on Day 1. Subjects will receive a pretreatment regimen of diphenhydramine 50 mg PO and ibuprofen 400 mg PO or diphenhydramine 50 mg PO and acetylsalicylic acid 325 mg PO 60 minutes before infusion.

Subjects will return for follow-up visits on Days 3 (± 1 day), 5 (± 1 day), 7 (± 1 day), 14 (± 3 days), 28 (± 3 days), 56 (± 7 days) and 100 (± 7 days). In addition, between clinic visits up to Day 7 (e.g., on Days 2, 4 and 6) subjects will receive a follow-up telephone call to ensure compliance with the Influenza Patient Reported Outcomes (FluPRO) Influenza Symptom Questionnaire and review any new or worsening signs or symptoms.

2.3 Primary Hypothesis

The primary objective is to assess the safety and tolerability of a single IV dose of VIS410 in subjects with uncomplicated influenza infection. There is no formal statistical testing for this protocol; differences between the treatments will be evaluated with 95% exact confidence intervals (CI) of the incidences of treatment-emergent AEs (TEAEs).

2.4 Study Sample Size

The study will enroll approximately 150 subjects. No formal sample size calculations were done for this study. The sample size is consistent with Phase 2a studies to assess safety and tolerability.

3 STUDY ENDPOINTS

3.1 Primary Endpoints

- The proportion of subjects with adverse events (AEs) and serious AEs (SAEs) following administration of VIS410
- The proportion of subjects with TEAEs including
 - Hypersensitivity reaction
 - Anaphylactic reaction
 - AEs of special interest (AESIs) following dosing

3.2 Secondary Endpoints

- The incidence, severity, and duration of signs and symptoms of influenza-like illness as assessed by the FluPRO questionnaire after a single IV dose of VIS410
- Percentage of participants requiring hospitalization for influenza-related complications
- Duration of hospitalization for influenza-related complications
- Percentage of participants with complications of influenza
- Percentage of participants with influenza A relapse/reinfection
- VIS410 PK parameters (C_{max} , t_{max} , $AUC_{0-\infty}$, AUC_{0-last} , $t_{1/2}$, V_d , CL) in serum
- The difference between VIS410 and placebo treatment groups in viral AUC from nasopharyngeal swabs
- The difference between VIS410 and placebo treatment groups in peak viral load and time to resolution of viral load from nasopharyngeal swabs

- Titer of anti-VIS410 antibody-positive samples

3.3 Exploratory Endpoints

- PK parameters (C_{\max} , t_{\max} , $AUC_{0-\infty}$, $AUC_{0-\text{last}}$, $t_{1/2}$, AUC ratio for nasopharyngeal: serum) of VIS410 from nasopharyngeal secretions
- Genotypic and phenotypic assessment to determine the emergence of VIS410-resistant viruses
- Correlations between serum and/or nasopharyngeal PK with viral load, clinical symptoms, presence of ADAs, and additional endpoints
- Titer of anti-influenza A antibodies by hemagglutinin inhibition assay (HAI) in serum
- Correlations between virology and safety parameters and/or additional parameters may be explored

4 GENERAL ANALYSIS DEFINITION

4.1 General Considerations

All statistical analyses and summary information are to be generated according to this SAP. Any deviations from this SAP will be documented in the CSR.

These descriptive statistics will be presented for continuous parameters: the number of subjects used in the calculation (n), mean, standard deviation (SD), median, minimum, and maximum values. For PK parameters, the geometric mean and coefficient of variance (CV) will also be presented. All continuous summaries will display the minimum and maximum value with the same number of decimals collected in the data. The median, mean, geometric mean and CV will display 1 additional decimal, and the SD and SE will display 2 additional decimals. For categorical variables, frequencies and percentages will be reported. All percentages will be reported to 1 decimal; all p-values will be reported to 3 decimals.

All temperature measurements will be presented as degrees Celsius. Degrees in Fahrenheit will be converted with this formula:

$$T_C = (T_F - 32) * (5/9),$$

where T_C is a Celsius temperature and T_F is a Fahrenheit measurement.

All statistical comparisons will be performed using 2-sided tests at the 0.05 significance level, unless specifically stated otherwise. All null hypotheses will be defined as no treatment difference. All p-values are presented for informational purposes only; there will not be any adjustments for multiple comparisons.

All analyses, summary tables, figures, and data listings will be generated with SAS version 9.4 or higher. Specialized PK software will be used for some PK analyses.

Baseline is defined as the latest non-missing measurement taken prior to study drug administration.

All summaries will be by actual visit, no visit windows for analysis will be defined. In general, summaries will be by treatment groups, and will include a combined VIS410 treatment group, in addition to the individual low dose (2000 mg) VIS410, high dose (4000 mg) VIS410, and Placebo treatment groups, unless specified differently. Summaries of disposition, other baseline data, and adverse events will also include an overall column.

4.2 Missing Data Conventions

Partial and missing AE and concomitant medication dates will be imputed with maximum conservatism. If the onset date is missing or partial, the date will be compared as far as possible with the date of first dose of study medication. If no month is present and it is in the same year as the date of first treatment, or the year and month are the same as the first treatment date, the onset date will be imputed as the date of first treatment. Otherwise it will be imputed as 01 January in the available year, or the first day of the month and year available. End dates will be imputed as 31 December in the available year, or the last day of the available month and year collected. Partial dates will be presented in listings, along with classifications of TEAE for AEs or Prior/Concomitant/Both for medications.

Missing data will generally be left as missing, except for partial and missing AE and concomitant medication dates. Special cases, e.g. below the limit of quantification, will be described in the sections that describe the specific parameter's analysis.

5 STUDY SUBJECTS

5.1 Analysis Populations

5.1.1 Intent-to-Treat Population

The intent-to-treat (ITT) population will include all subjects randomized to treatment.

5.1.2 Modified Intent-to-Treat Population

The mITT population will include all subjects who receive IV study drug and are confirmed influenza A positive by a molecular test at the central virological laboratory.

5.1.3 Safety Population

The safety population will include all ITT subjects who received IV study drug. The safety population summaries will be based on the actual treatment received.

5.1.4 Pharmacokinetic Population

The PK population will include all subjects who receive IV study drug and have at least 1 PK parameter that can be calculated. Nasopharyngeal swabs that are collected outside of the protocol defined sampling time points for PK (i.e. when influenza-like symptoms are present) will not be used to determine PK parameters. Nasopharyngeal PK parameters will only be calculated for the first 50 subjects enrolled.

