Study Time Point	Screening ¹	Day 1					Clinic Visit Day						
		Baseline ¹	Pre-dose	0 hour	End of Infusion	≥2 Hours from End of Infusion	3 (±1) ²	5 (±1) ²	7 (±1)	14 (±3)	28 (±3)	56 (±7)	100 (±7) FU/ET ³
Screening/Administrative Assessments													
Informed consent	X												
Inclusion/exclusion criteria	X												
Medical history and demographics	X												
Admission		X											
Discharge						X							
Nasopharyngeal swab for Rapid flu test ⁴	X												
Onset of symptoms interview	X												
Randomization		X											
Safety Assessments ⁵													
Supine ECG ⁶	X				X								
Vital signs ⁷	X	X ⁸			X	X	X	X		X	X	X	X
Body temperature ⁹	X	X ⁸			X	X	X	X	X	X	X	X	X
Physical exam	X												
Targeted physical exam ¹⁰		X ⁸				X	X	X	X	X	X	X	X
Urine pregnancy test ¹¹	X												X
Serology (HIV rapid test) ¹²	X												
Chemistry ¹³	X							X		X			X

Study Time Point	Screening ¹	Day 1					Clinic Visit Day						
		Baseline ¹	Pre-dose	0 hour	End of Infusion	≥2 Hours from End of Infusion	3 (±1) ²	5 (±1) ²	7 (±1)	14 (±3)	28 (±3)	56 (±7)	100 (±7) FU/ET ³
Hematology ¹³	X							X		X			X
Urinalysis ¹³	X							X		X			X
Instructions conmeds and FluPRO	X												
Observation in unit				X	X	X							
FluPRO completion ¹⁴		X					X			X			
FluPRO compliance						X	X	X	X				
FluPRO collection, review and reinstructions							X	X	X				
AESIs		X									X		X ¹⁵
Concomitant therapy, AEs ²		X											X
Collection of SAEs		X											X
Influenza complications		X											X
Study Agent Administration/Virologic/PK, and Immunogenicity Assessments													
Pretreatment medications – 1 hour (±5 min) prior to start of infusion ¹⁶			X										
VIS410/placebo infusion ¹⁷				X									
Serum PK			X ¹⁸		X ¹⁹		X	X	X	X	X	X	X
Nasopharyngeal swab ²⁰			X ¹⁸				X	X	X	X ^{21, 22}	X ^{21,22}	X ^{21,22}	X ^{21,22}
Serum ADA			X							X		X	X
Serum HAI sample			X							X	X		

¹ Screening and baseline activities may be performed on the same day.

² Subjects will have a follow-up phone call in the evening of the dosing day to ensure subjects' safety and well-being. In addition, between clinic visits up to Day 7 (e.g., Days 2, 4 and 6), subjects will receive a follow-up telephone call to ensure compliance with FluPRO Influenza Symptom Questionnaire and review any new or worsening signs or symptoms.

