¹⁷ Subjects will be observed during infusion and at least 2 hours after completing the infusion of VIS410 to allow monitoring for possible hypersensitivity reactions. VIS410 will be administered over 2 hours. Infusion time can be extended at discretion of the Investigator up to 4 hours based on local infusion-related symptoms. If any serious systemic reactions occur, the infusion of VIS410 can be slowed or stopped at the discretion of the Investigator.

¹⁸ Within 1 hour prior to VIS410 administration.

¹⁹ Sample collected within 30 minutes after completing the infusion of VIS410/placebo.

²⁰ Nasopharyngeal swabs will be obtained from both nostrils (1 swab per nostril).

²¹ Will be done for the first 50 subjects enrolled only.

²² If a subject presents with or reports influenza-like illness, additional swabs (1 swab per nostril) should be taken (see Section 7.1.5).

LIST OF ABBREVIATIONS AND DEFINITIONS OF TERMS

Abbreviation	Definition
ADA	Anti-drug antibody
AE	Adverse event
AESI	Adverse event of special interest
AUC	Area under the curve
AUC _{0-∞}	Area under the concentration-time curve extrapolated to infinity
AUC _{0-last}	Area under the concentration-time curve from time 0 to the last measurable concentration
CD-1	Cluster of differentiation 1
CL	Clearance
C _{max}	Maximum serum concentration
CRO	Contract Research Organization
DBA	Dilute Brown Non-Agouti
DBP	Diastolic blood pressure
DMID	Division of Microbiology and Infectious Diseases
DSMB	Data Safety Monitoring Board
EC ₅₀	Half-maximal effective concentration
EDC	Electronic data capture system
GCP	Good Clinical Practice
GI	gastrointestinal
GLP	Good Laboratory Practice
HA	Hemagglutinin
HAI	Hemagglutination inhibition assay
HIV	Human immunodeficiency virus
ICF	Informed Consent Form
ICH	International Conference on Harmonization
IEC	Independent Ethics Committee
IgG1	Immunoglobulin G1
IRB	Institutional Review Board
ITT	Intent-to-treat
IV	Intravenous
LSLV	Last Subject Last Visit
MedDRA	Medical Dictionary for Regulatory Activities
mITT	Modified intent-to-treat
NOAEL	No-observed-adverse-effect level
NSAID	Non-steroidal anti-inflammatory drug
PK	Pharmacokinetic
PO	Oral (by mouth)
qRT-PCR	Quantitative reverse transcriptase polymerase chain reaction
SAE	Serious adverse event
SAP	Statistical analysis plan
SBP	Systolic blood pressure
SUSAR	Suspected unexpected serious adverse reaction
t _{1/2}	Elimination half-life
TCID ₅₀	Half-maximal tissue culture infective dose

Abbreviation	Definition

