9.2 RANDOMIZATION AND BLINDING

This will be a double-blind study. The Contract Research Organization (CRO) and site study personnel and Visterra personnel will not be aware of which treatment (active study drug or placebo) the subjects have been given. Subjects will not be aware of which treatment they have been administered.

Subjects will be randomized 1:1:1 to receive VIS410 2000 mg, VIS410 4000 mg, or placebo. A randomization list with randomization numbers will be created. The randomization numbers must be used sequentially to ensure an overall balance; no randomization number can be skipped. Allocation of each subject to a given treatment sequence will be described in a randomization list prepared by Visterra or designee. The randomization will be balanced using randomly permuted blocks across the treatment groups.

The randomization list will not be available to the subjects, Investigators, (blinded) monitors, or employees of the clinical center involved in the management of the study before unblinding of the data, unless in case of emergency. The Sponsor's clinical team will also be blinded during the study as they will not have direct access to the randomization list. The CRO performing data management and statistical activities will receive a copy of the randomization list during database lock. Other team members will not have access to any data that could lead to unblinding.

Unblinding of the individual subject's treatment by the Investigator should be limited to medical emergencies or urgent clinical situations in which knowledge of the subject's study treatment is necessary for clinical management. In such cases, the Investigator must first attempt to contact the Medical Monitor or appropriate back up (contact information as detailed in a separate document), to discuss and agree to the need for unblinding to occur. The Medical Monitor or designee will answer calls 24 hours a day, 7 days a week, 365 days of the year. In situations in which the Investigator has tried, but is unable to reach the Medical Monitor, they should use their best judgment, based on the nature and urgency of the clinical situation, and may proceed with unblinding without having successfully reached and discussed the situation with the Medical Monitor.

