- $AUC_{0-\infty}$: area under the serum concentration-time curve from time 0 extrapolated to infinity
- $AUC_{0-\text{last}}$: area under the serum concentration-time curve from time 0 to the last measurable concentration
- $t_{1/2}$: terminal elimination half-life
- CL: total clearance
- V_d : volume of distribution

PK data from this study will be also analyzed by population PK modeling.

Nasopharyngeal Secretion Pharmacokinetics

Nasopharyngeal secretion concentrations and the computed PK parameters will be listed by subject for VIS410. Summary statistics of nasopharyngeal secretion concentrations and PK parameters will be presented including means, geometric means, standard deviations, CV, medians and ranges, as appropriate. Additional analyses and summaries may be generated as appropriate.

The following PK parameters will be determined for VIS410 from nasopharyngeal secretions:

- C_{\max} : maximum concentration observed from nasopharyngeal secretions
- T_{\max} : time of C_{\max}
- $AUC_{0-\infty}$: area under the nasopharyngeal secretion concentration-time curve from time 0 extrapolated to infinity
- $AUC_{0-\text{last}}$: area under the nasopharyngeal secretion concentration-time curve from time 0 to the last measurable concentration
- $t_{1/2}$: terminal elimination half-life
- Ratio of nasal:serum AUC

Additional PK parameters may be determined as appropriate.

9.3.4 *Viral Shedding*

Additional sensitivity analysis may be conducted excluding subjects that received concomitant antiviral therapy during the course of the study.

- One-way analysis of variance (ANOVA) (with treatment group as the factor) or other appropriate statistics detailed in the SAP to assess the difference between VIS410 treatment groups vs placebo in the area under the viral load-time curve (AUC) for influenza virus based on quantification of viral load from nasal swabs

- Descriptive statistics of the area under the viral load-time curve (AUC) for influenza virus based on quantification of viral load from nasopharyngeal swabs by treatment group.
- Descriptive statistics of the time to resolution of viral load and of the peak viral load by treatment group.

The mITT population will be used for the summaries.

9.3.5 *Signs and Symptoms of Influenza*

The difference between VIS410 and placebo will be assessed as outlined below.

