10.2 Nasopharyngeal Secretion Pharmacokinetics

Individual concentrations versus time profiles will be plotted on both linear and logarithmic scales in all subjects. Mean (\pm SD) or median concentrations versus time profiles will be plotted on both linear and logarithmic scales for the first 50 subjects enrolled that have the full PK profile collected. PK parameters listed above ([Section 11](#)) will be determined for VIS410 from nasopharyngeal secretions in the first 50 subjects enrolled only. Summary statistics of nasopharyngeal concentrations (first 50 subjects and in all subjects) and PK parameters (first 50 subjects only) will be presented by nominal time of collection including n, mean, geometric mean, standard deviation, CV, median and ranges, as appropriate. Additional analyses and summaries may be generated as appropriate.

Correlations between serum PK parameters and nasopharyngeal PK parameters will be presented. The 2 ratios of nasal AUC/serum AUC from the Day 3 visit until the last measurement and to infinity, will also be summarized with these statistics.

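### SAP 5.1.4, 10 and 10.2 limit every nasal PK parameter to the first 50 enrolled, undeclared in SAP 16.1, although a Day 3-7 maximum and partial AUC could be derived in all of about 100 VIS410 subjects

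*SAP*

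**What the plan says.** SAP 5.1.4 defines the PK population and adds: "Nasopharyngeal PK parameters will only be calculated for the first 50 subjects enrolled". SAP 10 repeats the limit for its nasal parameters. SAP 10.2 treats concentrations and parameters differently: "Summary statistics of nasopharyngeal concentrations (first 50 subjects and in all subjects) and PK parameters (first 50 subjects only"). It also plots individual nasal profiles in all subjects, keeps mean or median plots for the first 50 because they have the complete profile, and plans correlations between serum and nasal PK parameters.

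In protocol Table 1, nasopharyngeal swabs are scheduled pre-dose and on Days 3, 5, 7, 14, 28, 56 and 100. Only the last four carry footnote 21: "Will be done for the first 50 subjects enrolled only". Serum PK samples are scheduled on Days 3, 5 and 7 in every subject.

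The protocol sets no first-50 limit on nasal parameters. Section 7.2.3 lists them without one, and section 9.3.3 says only: "The following PK parameters will be determined for VIS410 from nasopharyngeal secretions". SAP 16.1, which records changes from the protocol-specified analyses, does not mention the limit.

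**The concern.** The sampling restriction and the parameter restriction do not match. Swabbing is limited to the first 50 only from Day 14 onwards, but the SAP applies the same limit to every nasal parameter, including ones that could be computed from the Day 3, 5 and 7 swabs that everyone has. About two-thirds of VIS410 subjects therefore receive no nasal exposure parameter, although their samples are already to be assayed and reported.

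At stake are exploratory analyses: the serum-nasal parameter correlation in SAP 10.2, and any use of nasal PK under the SAP 3.3 endpoint that relates serum and/or nasal PK to viral load. SAP 11.2 and 11.3 derive the viral load parameters through the Day 7 visit in all mITT subjects, so a Day 3-7 nasal exposure measure would cover nearly the same period. Protocol 4.2 adds some interest, since it says that doses above 2300 mg may be needed to reach adequate concentration at the site of infection for less susceptible strains.

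Separately, a restriction absent from the protocol should appear in SAP 16.1.

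**Working it through.** The documents give no precision or power figure for nasal PK (SAP 2.4: "The study will enroll approximately 150 subjects. No formal sample size calculations were done for this study"), so there is nothing of the plan's own to reproduce.

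**Subjects.** Allocation is from protocol 9.2: "Subjects will be randomized 1:1:1 to receive VIS410 2000 mg, VIS410 4000 mg, or placebo".

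- VIS410 overall: 150 × 2/3 = 100, about 50 per dose.
- VIS410 among the first 50: 50 × 2/3 = 33.3, about 17 per dose. With one central list and blocks of 3 to 12 (an assumption; block size is not stated) the count would be 32 to 35.
- VIS410 subjects without any nasal parameter: 100 − 33.3 = 66.7.

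**Scheduled post-dose nasal samples in VIS410 subjects.**

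- First 50: 33.3 × 7 = 233 (Days 3, 5, 7, 14, 28, 56, 100).
- Remainder: 66.7 × 3 = 200 (Days 3, 5, 7).
- Outside parameter calculation: 200/433 = 46% of all post-dose samples; 200/300 = 67% of the Day 3-7 samples.
- Left out of all reporting: none, because SAP 10.2 summarises and plots concentrations in all subjects.

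**Which parameters need the late swabs.** Assume mono-exponential decline and a nasal half-life equal to the 12.9-day mean serum value in protocol 1.3, with a range of 8 to 20 days. Day 7 is 6 days after dosing. The share of AUC0-inf lying beyond the last swab is exp(−ln 2 × time/half-life).

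| Assumed half-life (days) | Share beyond Day 7 | Share beyond Day 100 | Day 3-7 span in half-lives |
|---|---|---|---|
| 8 | 59% | 0.02% | 0.50 |
| 12.9 | 72% | 0.5% | 0.31 |
| 20 | 81% | 3.2% | 0.20 |

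Three samples over about 0.3 of a half-life cannot support t1/2 or AUC0-inf. AUC0-last ending at Day 7 is also a different quantity from AUC0-last on a schedule running to Day 100. The observed Day 3-7 maximum and the Day 3-7 partial AUC use no sample after Day 7.

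**Gain from about 33 to about 100 subjects.**

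- Smallest correlation with two-sided p<0.05: r = t/√(n − 2 + t²). For n = 33, t = 2.040 and r = 2.040/√(31 + 4.16) = 0.34. For n = 100, t = 1.984 and r = 1.984/√(98 + 3.94) = 0.20.
- Interval width on the log scale for a dose group: √(50/17) = 1.71 times wider with 17 than with 50.
- The CV of nasal parameters is not given. Assuming 60%, the log SD is √ln(1 + 0.36) = 0.555. A 95% interval for one geometric mean is then ×0.75 to ×1.33 with 17 subjects and ×0.85 to ×1.17 with 50.
- For a 4000:2000 mg ratio, which the SAP does not plan and which serves here only as a yardstick:

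| Assumed CV | 17 per dose | 50 per dose |
|---|---|---|
| 40% | ×0.76 to ×1.31 | ×0.86 to ×1.17 |
| 60% | ×0.68 to ×1.47 | ×0.80 to ×1.25 |
| 100% | ×0.56 to ×1.79 | ×0.72 to ×1.39 |

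**The case against.** The restriction has a rationale. Only the first 50 are sampled beyond Day 7, and keeping one parameter set on one sampling scheme is defensible. That stands in full for AUC0-last, AUC0-inf and t1/2.

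The added measures are also modest. There is no post-infusion nasal swab on Day 1, so the Day 3-7 maximum is the largest of three values and the partial AUC is a weighted average of the same three. This limits the gain but does not remove it: a per-subject exposure value is needed for any correlation, and the by-visit summaries do not supply one.

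Several stronger readings are tempting, and the documents do not support them:

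- A reader might infer that two-thirds of the nasal exposure data are thrown away. Concentrations are summarised and plotted in everyone, and an optional population PK model (SAP 10) may use nasal data with no first-50 limit. Two-thirds is right for VIS410 subjects and for Day 3-7 samples, not for all nasal samples (46%).
- A reader might infer that the comparison of nasal exposure between doses rests on a third of the subjects. The concentration summaries already show both doses in about 50 subjects each. SAP 10.2 is descriptive and plans no nasal ratio or interval. Protocol 4.2 also justifies 4000 against 2000 mg by separation in systemic exposure, and serum PK is planned in all subjects.
- A reader might infer that a specified nasal PK-viral load analysis is underpowered. SAP 11.5 names only serum AUC and Cmax as exposure variables, and the SAP 3.3 endpoint can be met with serum alone.
- A reader might infer bias because the first 50 come from the earliest sites. The documents say nothing about the order in which sites open or about nasal PK differing by region.

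**Conclusion.** The point holds in a limited form. The first-50 limit reaches further than the sampling design requires, and SAP 16.1 does not declare it. For the observed Day 3-7 maximum and the Day 3-7 partial AUC, about 100 VIS410 subjects could contribute instead of about 33. For AUC0-last, AUC0-inf and t1/2 the limit is right.

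The size is a threefold increase in subjects for exploratory correlations, with the critical correlation falling from 0.34 to 0.20 and log-scale intervals about 1.7 times narrower. The counts assume about 150 enrolled, even allocation and complete Day 3, 5 and 7 swabs; missed swabs would lower the figure of 100. The interval examples rest on assumed CVs, and the extrapolation shares on an assumed nasal half-life. No primary or secondary conclusion depends on this, so it is a minor improvement.

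**What to change.** In SAP 5.1.4, 10 and 10.2:

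1. Derive the observed nasal maximum over Days 3-7 and the nasal partial AUC from the Day 3 to the Day 7 swab in all VIS410 subjects with Day 3, 5 and 7 swabs, together with the matching Day 3-7 serum AUC and the nasal:serum ratio. The visit windows (Day 3 ± 1, Day 7 ± 1) let the actual span run from 2 to 6 days, so state a common interval or divide the area by elapsed time.
2. Use these measures for the serum-nasal parameter correlation in SAP 10.2 and for any nasal PK-viral load correlation under SAP 3.3.
3. Keep AUC0-last, AUC0-inf and t1/2 in the first 50, and list that restriction in SAP 16.1 with its reason.

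The cost is SAP wording, one extra PK run and one more parameter set in Table 14.4.1.4. No new samples or assays are needed. The Day 3-7 measures rest on three samples per subject, and the report should say so.
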